### **Study Device**

The sustained-release depot is a single-use insert containing 0.4 mg of active dexamethasone designed for implantation through the punctum in the canaliculus. The device was approved by the FDA for the treatment of ocular inflammation and pain in association with ocular surgery. The insert's composition is polyethylene glycol (PEG) and employs hydrogel technology to deliver dexamethasone. The insert is also conjugated with fluorescein allowing for visualization of the insert after it is inserted into the canaliculus. With contact of fluid (hydration), the insert swells to securely conform to the canicular location, allowing direct delivery of the

preservative-free dexamethasone on to the ocular surface over the course of 30 days. Over time, with continuous hydrolysis, the insert gradually softens and degrades and is eventually cleared through the nasolacrimal drainage system without the need for removal.

### **Statistical Analysis**

All statistical analysis was performed using Prism 9 software (GraphPad Software, Inc.). Repeated measures analysis of variance was performed to compare the values at each time point in each group. Post hoc analyses were also performed with Bonferroni correction to directly compare the mean values at each time point in comparison to baseline. A *P* value less than 0.05 was considered statistically significant.

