### **Main Outcome Measures**

The primary outcome measure was the mean change in corneal surface staining (guided by use of fluorescein and lissamine green) at weeks 1, 2, 4, 8 and 12 based on the NEI grading scale. Corneal fluorescein staining was graded from 0 to 3 (none to heavy) in five regions of the cornea and summed for a total score.

All secondary outcome measures followed the same timeline with comparison at weeks 1, 2, 4, 8 and 12 in comparison to baseline. Secondary outcome measures included the mean change in tear break-up time (TBUT), the mean change in conjunctival staining (graded 0-3 in 6 regions), the mean change in tear osmolarity as measured by TearLab, the mean change in DEQ-5, the mean change in meibomian gland scores as measured by quality of meibum expression, the mean change in best-corrected distance visual acuity (BCDVA) as measured by ETDRS chart and the mean change in Schirmer's score as measured by a Schirmer's test strip.

Meibomian gland scoring involved grading the quality of expression (0-3) from 15 glands along the lower eyelid including temporal, central and nasal. For scoring, 3 was representative of clear, liquid secretions and 0 was no secretions. The DEQ-5 Dry Eye Questionnaire was used to evaluate symptoms and characterize severity of discomfort, dryness and tearing. Possible scores ranged from 0 to 22 with higher scores representing worse symptoms.

On the screening visit and the initiation of therapy including implantation of the dexamethasone insert in the study group, a physician ease of insertion questionnaire was also completed by the physician implanting the device. All device-related complications were recorded. All subject-reported adverse events were recorded at each study visit.

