## **RESULTS**

### **Patient Demographics**

Sixty eyes of 30 subjects were successfully enrolled into the study including 20 eyes of 10 subjects in the dexamethasone/cyclosporine group, 22 eyes of 11 subjects in the loteprednol/cyclosporine group and 18 eyes of 9 subjects in the cyclosporine monotherapy group. All 3 groups were summarized by baseline characteristics, which are shown in Table 2.

None of the three groups, including the study and two control groups met the primary endpoint. In the dextenza group, the mean baseline corneal staining score was  $0.5 \pm 1.0$  with 70% ( $n=14$ ) without evidence of corneal staining at baseline. The mean score at weeks 4, 8 and 12 was  $0.6 \pm 1.0$  ( $P = 0.99$ ),  $0.5 \pm 1.1$  ( $P = 0.99$ ) and  $0.7 \pm 1.4$  ( $P = 0.97$ ), respectively. In the loteprednol group, the mean baseline corneal staining score was  $0.8 \pm 1.5$  with 64% ( $n=14$ ) without corneal staining at baseline. At weeks 4, 8 and 12, the mean score was  $0.9 \pm 0.9$  ( $P = 0.99$ ),  $0.0 \pm 0.0$  ( $P = 0.06$ ) and  $0.6 \pm 1.0$  ( $P = 0.78$ ), respectively. In the cyclosporine monotherapy group, the mean baseline corneal staining score was  $0.5 \pm 0.5$  with 50% ( $n=9$ ) of eyes absent of any corneal staining at baseline. There was no significant change in corneal staining at any time point with a mean score of  $1.1 \pm 1.4$  ( $P = 0.26$ ),  $0.3 \pm 0.6$  ( $P = 0.63$ ) and  $0.5 \pm 0.7$  ( $P = 0.99$ ) at weeks 4, 8 and 12, respectively. These results, in addition to comparisons of other outcome measures, are summarized in Table 3.

There was no significant change in conjunctival staining, Schirmer scores, TBUT, tear osmolarity or meibomian gland scores at any of the follow-up time points in comparison to baseline in all three groups. These results are summarized and also demonstrated in Table 3.

Across all visits, the mean IOP remained stable in all three groups. In the cyclosporine monotherapy group, there were no instances of IOP elevation  $>10$  mmHg above baseline. Similarly, in the dextenza and loteprednol groups, there were no instances of IOP elevation  $>10$

mmHg above baseline at any time point. There were no canalicular-related complications or adverse events related to implantation of the dexamethasone insert. No patients required removal of the insert.

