**Table 2 - Results**

Parameter	Dextenza + Cyclosporine	Loteprednol + Cyclosporine	Cyclosporine monotherapy
Corneal staining			
• Baseline	0.6 ± 1.0	0.8 ± 1.5	0.5 ± 0.5
• 1 month	0.6 ± 1.0	0.9 ± 0.9	1.1 ± 1.4
• 2 month	0.5 ± 1.1	0.0 ± 0.0	0.3 ± 0.6
• 3 month	0.7 ± 1.4	0.6 ± 1.0	0.5 ± 0.7
Conjunctival staining			
• Baseline	0.5 ± 1.8	1.5 ± 1.8	0.4 ± 0.6
• 1 month	0.3 ± 0.6	0.9 ± 1.4	0.5 ± 0.7
• 2 month	0.4 ± 0.8	0.8 ± 1.8	0.3 ± 0.6
• 3 month	0.8 ± 1.7	1.0 ± 1.6	0.7 ± 1.4
Schirmer scores (mm/5 min)			
• Baseline	14.9 ± 10.3	10.3 ± 7.2	11.6 ± 10.5
• 1 month	15.4 ± 10.1	12.9 ± 9.1	10.1 ± 8.5
• 2 month	15.8 ± 9.4	12.4 ± 8.4	10.8 ± 6.4
• 3 month	12.3 ± 7.1	10.1 ± 6.0	9.6 ± 5.5
Tear breakup time (seconds)			
• Baseline	6.6 ± 2.2	5.4 ± 1.5	5.7 ± 3.3
• 1 month	8.0 ± 3.6	6.1 ± 2.8	7.4 ± 3.7
• 2 month	7.7 ± 3.1	6.2 ± 2.2	7.1 ± 3.4
• 3 month	7.7 ± 2.5	6.1 ± 2.4	7.3 ± 3.6
Tear osmolarity			
• Baseline	295.5 ± 17.4	311.3 ± 19.8	306.9 ± 28.4
• 1 month	304.4 ± 30.1	307.7 ± 17.3	307.9 ± 24.2
• 2 month	303.9 ± 22.1	300.1 ± 19.2	295.3 ± 20.7
• 3 month	299.5 ± 16.2	304.4 ± 28.7	304.6 ± 19.6
Meibomian gland scores			
• Baseline	8.7 ± 2.4	7.1 ± 2.1	9.2 ± 2.6
• 1 month	7.6 ± 1.8	6.7 ± 2.5	7.2 ± 1.4
• 2 month	8.3 ± 2.0	6.3 ± 2.6	8.2 ± 2.2
• 3 month	8.7 ± 2.0	6.0 ± 2.3	7.3 ± 1.4

**Table 2.** Results of clinical parameters are summarized with the mean and standard deviation demonstrated at weeks 4, 8 and 12 in comparison to baseline.

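### Repeated-measures ANOVA, apparently by eye, is a poor fit for a corneal staining score that is mostly zero; the one checkable P value (0.06) is unreliable in either direction.

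*SAP*

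**What the plan says.** The SAP's Statistical Analysis section gives the whole method: "Repeated measures analysis of variance was performed to compare the values at each time point in each group". It continues: "Post hoc analyses were also performed with Bonferroni correction to directly compare the mean values at each time point in comparison to baseline". Its significance rule is that a P "value less than 0.05 was considered statistically significant". It does not state the number of comparisons in the Bonferroni correction, a check of distribution, or how two eyes of one patient are handled.

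The primary score is an integer per eye: "Corneal fluorescein staining was graded from 0 to 3 (none to heavy) in five regions of the cornea and summed for a total score". The possible range is therefore 0 to 15. Change is to be assessed "at weeks 1, 2, 4, 8 and 12 based on the NEI grading scale", which is five follow-up visits. Table 2 gives the "mean and standard deviation demonstrated at weeks 4, 8 and 12 in comparison to baseline", which is three.

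The SAP's Results (Patient Demographics) count staining by eye. The insert arm has 14 of 20 eyes at zero at baseline. The loteprednol arm has 14 of 22 eyes "without corneal staining at baseline". The monotherapy arm has 9 of 18 at zero. Loteprednol goes from 0.8 ± 1.5 at baseline to 0.9 ± 0.9 at week 4 (P = 0.99), 0.0 ± 0.0 at week 8 (P = 0.06) and 0.6 ± 1.0 at week 12 (P = 0.78). The conclusion is: "None of the three groups, including the study and two control groups met the primary endpoint".

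**The concern.** A comparison of means under normal theory suits this score badly. Most eyes are at the floor, a few high scores supply nearly all the variance, and one visit has no variance at all. Treating the two eyes of a patient as separate units would also overstate the information in arms of 9 to 11 patients. These two faults can push the P value in opposite directions: a few high scores inflate the standard error, while ignoring the pairing of eyes usually shrinks it. The loteprednol week 8 result is the smallest corneal staining P value printed and lies next to the 0.05 threshold, so there the choice of test and unit matters most. At stake is whether that P value can be relied on, whichever side of 0.05 it falls.

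**Working it through.** **Inputs** (SAP Results and Table 2): zeros at baseline 14/20, 14/22 and 9/18; loteprednol baseline 0.8 ± 1.5, week 8 0.0 ± 0.0, P = 0.06; 22 eyes of 11 patients. Tests are assumed two-sided, because the SAP does not say.

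**1. Share of zeros.** (14 + 14 + 9)/60 = 37/60 = 62%.

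**2. Shape of the data.**
- Monotherapy: 9 positive integer scores in 18 eyes with a mean that rounds to 0.5 allow a total of only 9. The data are nine 0s and nine 1s.
- Loteprednol: 8 positive scores that round to 0.8 ± 1.5 over 22 eyes allow nine integer patterns, from 6,4,2,1,1,1,1,1 to 5,4,4,1,1,1,1,1. In each, one to three eyes scoring 4 to 6 drive the SD.

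**3. Reproducing the printed 0.06.** If every week 8 score is zero, the drop from baseline equals the baseline score.
- t = 0.8/(1.5/√22) = 2.50 on 21 df, P = 0.0207.
- Times 3 (weeks 4, 8, 12) = 0.062, which matches 0.06. Times 5 = 0.104, which does not.
- Over the nine patterns, times 3 gives 0.049 to 0.077 and times 5 gives 0.081 to 0.129.

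The best reading is a by-eye contrast corrected for three visits. It is not proof. If the pattern were 6,4,2,1,1,1,1,1 with each stained eye in a different patient, the 11 patient means would be 3, 2, 1, five of 0.5 and three of 0. That gives mean 0.773, SD 0.932, t = 2.75 on 10 df, P = 0.0205, times 3 = 0.061.

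**4. Exact test by eye, same correction.** If k stained eyes are measured at week 8 and all fall to zero, the sign test and the signed-rank test both give P = 2 × 0.5^k.

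| k | P | times 3 | times 5 |
|---|---|---|---|
| 8 | 0.0078 | 0.023 | 0.039 |
| 7 | 0.0156 | 0.047 | 0.078 |
| 6 | 0.0313 | 0.094 | 0.156 |
| 5 | 0.0625 | 0.188 | 0.313 |
| 4 | 0.125 | 0.375 | 0.625 |

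The SAP does not give the number of eyes measured at week 8.

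**5. Exact test by patient.** Eight stained eyes belong to 4 to 8 patients, so the same table applies with k as patients. Times 3 runs from 0.023 to 0.375, and is below 0.05 only with 7 or 8 patients.

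**6. t test on 11 patient means.** With between-eye correlation r, the SD of a patient mean is 1.5 × √((1 + r)/2).
- r = 0: SD 1.06, P = 0.031, times 3 = 0.094.
- r = 0.5: SD 1.30, P = 0.068, times 3 = 0.205.
- r = 1: SD 1.5, P = 0.107, times 3 = 0.322.

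The documents do not give r. A negative r, with stained eyes mostly in different patients, would give smaller values, as in the example in step 3.

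**7. Floor of the exact test in the insert arm.** There, 20 − 14 = 6 eyes were stained at baseline. If all 6 cleared and no eye worsened, P = 2 × 0.5^6 = 0.031, times 3 = 0.094. By patient (3 to 6 patients) the best case is no smaller.

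**The case against.** The strongest objection is to the reading that a reader might infer from step 4: that a proper test gives 0.02, so the loteprednol arm met the endpoint and the primary conclusion is wrong. The documents do not support that. The 0.023 needs a factor of 3, all 8 stained eyes measured at week 8, and independent eyes; by patient it is the lower end of the range. The P value concerns one control arm at one visit. Means of 0.9 at week 4 and 0.6 at week 12 do not show a sustained fall, and no rule makes a single visit sufficient. The insert arm has P values of 0.97 to 0.99. The Protocol's Rationale asks for comparisons between arms, which no within-arm P value answers.

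A reader might also infer that every staining P value is wrong. That is not shown. Only one of the nine printed corneal P values can be recomputed, because the others need paired changes that the documents do not give. Conjunctival P values are not printed.

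Two further points stand. A zero-variance visit does not by itself invalidate a contrast built on change scores. One compatible pattern gives 0.049 under the same t test, so the position relative to 0.05 is partly a matter of rounding. The SAP's Discussion also concedes that samples were small and that staining was not an inclusion criterion.

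None of this makes the method suitable. It limits what can be concluded from the 0.06.

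**Conclusion.** The point holds as a weakness of method, not as a reversal of the result. The primary score is 62% zeros at baseline and is analysed by means, apparently with eyes as independent units. The printed P = 0.06 could be as low as 0.023 or as high as 0.375 after the same times 3 correction, depending on the test and on how the 8 stained eyes fall among patients. That range assumes two-sided tests, three comparisons and all 8 stained eyes measured at week 8; missing eyes would raise the exact values. The present figures establish neither a missed effect nor a different overall primary verdict. The sequence 0.9, 0.0 ± 0.0, 0.6 could also reflect missing or mis-entered data, so the all-zero cell needs checking before any test is re-run.

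**What to change.** For corneal and conjunctival staining, reduce the data to one value per patient, for example the mean of both eyes, and then:

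- Make the between-arm difference in change the main comparison, by permutation test. The Protocol (Study Description and Duration) calls the study non-randomized and the SAP (Patients) calls it randomized. Reconcile this, because without randomization the test rests on assumed exchangeability of patients.
- Give exact within-arm tests as supportive only.
- Report patients improved, unchanged and worse, the number of eyes measured at each visit, and the number of Bonferroni comparisons.
- Check the loteprednol week 8 cell against source first.
- Label the re-analysis as post hoc, since it follows sight of the 0.06.

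The cost is a re-analysis of existing data and new SAP wording. The real downside is the floor in step 7: with 6 stained eyes in the insert arm, an exact within-arm test cannot show improvement below 0.05 after a times 3 correction (0.094 at best, even by eye). A non-significant exact result there would say little, which is a further reason to keep those tests supportive.

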Intracanalicular Dexamethasone used in conjunction with Restasis (cyclosporine ophthalmic emulsion) for the treatment of signs and symptoms of dry eye disease as compared to Restasis with Lotemax (loteprednol etabonate ophthalmic suspension 0.5%) and Restasis monotherapy.

[name] STUDY

Compound:

DEXTENZA® (dexamethasone ophthalmic insert) 0.4 mg for intracanalicular use

Study Name:

[name] STUDY

Protocol Number:

TC-2020-DexRes

Clinical Phase:

Open label prospective

Date of Issue:

01/11/2021

Primary Investigator:

[name]

Site Name & Location:

Cleveland Eye Clinic
[name],
[name]

[name] STUDY V2

CLINICAL STUDY PROTOCOL SYNOPSIS

TITLE	Intracanalicular Dexamethasone used in conjunction with Restasis (cyclosporine ophthalmic emulsion) for the treatment of signs and symptoms of dry eye disease as compared to Restasis with Lotemax (loteprednol etabonate ophthalmic suspension 0.5%) and Restasis monotherapy.
SITE LOCATION(S)	Cleveland Eye Clinic [name]
PRINCIPAL INVESTIGATOR	[name]
OBJECTIVE(S)	To evaluate the benefit of treatment with a physician administered intracanalicular dexamethasone insert in patients with dry eye who are beginning treatment with Restasis (cyclosporine ophthalmic emulsion) to reduce the signs and symptoms of dry eye disease.
STUDY DESIGN	Prospective Open-label Interventional Study
STUDY DURATION	6 months including screening and enrollment
ESTIMATED STUDY COMPLETION DATE	3 months after date of insertion
POPULATION	
Sample Size:	30 patients (60 eyes)
Target Population:	Patients with dry eye who are about to begin treatment with Restasis bilaterally to reduce the signs and symptoms of dry eye disease and who have not been on topical immunomodulation for a minimum of 3 months prior to the start of the study.
TREATMENT(S)	

[name] STUDY V2

Study Drug	Sustained Release Dexamethasone, 0.4 mg
Dose/Route/Schedule:	All patients will be prescribed Restasis BID for both eyes who have not been on topical immunomodulation for a minimum of 3 months, and who would benefit from addition of topical pharmacotherapy (immunomodulation). There will be 3 groups. 10 patients will receive Restasis BID and Dextenza in both eyes, 10 patients will receive Restasis BID for 12 weeks and Lotemax BID for one month in both eyes and 10 patients will receive Restasis BID monotherapy.

Screening/ Prescription

- 1-week
- 2-week
- 1 month
- 2 month
- 3 month

ENDPOINT(s)

PRIMARY:

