2. STUDY OBJECTIVES

2.1. Primary Objective

- Mean change in ocular surface staining (sodium fluorescein and lissamine green) from baseline at week 1, week 2, week 4, week 8 and week 12 as measured by the NEI grading scale

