4.2. Treatment Logistics and Accountability

4.2.1. Packaging, Labeling, and Storage

Intracanalicular dexamethasone insert must be stored in a secure area accessible only to the Investigator and their designee(s) and refrigerated and stored between 2° C and 8° C. Intracanalicular dexamethasone insert contains 0.4 mg dexamethasone and is designed to provide a sustained and tapered release of therapeutic levels of dexamethasone to the ocular surface for up to 30 days for the reduction of post-surgical inflammation and pain associated with ocular surgery. Dexamethasone is an anti-inflammatory 9-fluoro-glucocorticoid (also termed a glucocorticoid agonist) and is the active

ingredient found in MAXIDEX® 0.1% (dexamethasone ophthalmic suspension), which contains approximately 50 µg of dexamethasone per drop.

Study inserts will be supplied by Ocular Therapeutix in a sealed foil pouch containing one intracanalicular dexamethasone insert in a foam carrier.

Study inserts will be shipped to the site via overnight shipping using cold packs to maintain a temperature of 2° to 8° C. The Investigator, or an approved representative (e.g. pharmacist), will ensure that all study drug inserts are stored in a secured area, under recommended storage conditions and in accordance with applicable regulatory requirements. The shipping box is to be opened and stored immediately at the site in a refrigerator intended for investigational products at a temperature of 2° to 8°C.

When the insert is removed from the refrigerator, it should be visually inspected. Exposure of the insert to temperatures outside these limits is not recommended. Records of actual storage conditions (i.e. temperature log) at the study site must be maintained; and must include a record of the dates, when the refrigerator was checked, the initials of person checking, and the temperature.

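### The primary outcome is tested at up to five visits in each of three groups, with no deciding visit, no correction across groups and no between-group test, so a group can meet it by luck more often than 5% allows

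*SAP*

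**What the plan says.** Protocol 2.1 sets the primary as mean change in staining "from baseline at week 1, week 2, week 4, week 8 and week 12 as measured by the NEI grading scale". The SAP (Main Outcome Measures) narrows it to corneal staining and keeps the same list, "at weeks 1, 2, 4, 8 and 12 based on the NEI grading scale". Neither document ranks the visits.

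The SAP's Statistical Analysis section gives three rules:

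- The main model: "Repeated measures analysis of variance was performed to compare the values at each time point in each group". It is thus fitted one group at a time.
- The follow-up tests, visit by visit: "Post hoc analyses were also performed with Bonferroni correction to directly compare the mean values at each time point in comparison to baseline". The number of comparisons is not given.
- The threshold: "A *P* value less than 0.05 was considered statistically significant". Sidedness is not given.

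No between-group test is described. The Results (under Patient Demographics) then give a verdict by group: "None of the three groups, including the study and two control groups met the primary endpoint". The Discussion adds that the endpoint was improvement in corneal staining, but gives no visit, number of visits or size of change. Staining results appear only for weeks 4, 8 and 12.

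On steroid exposure, Protocol 4.2.1 describes release of "therapeutic levels of dexamethasone to the ocular surface for up to 30 days", and the Synopsis prescribes "Lotemax BID for one month in both eyes". Restasis runs for 12 weeks.

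**The concern.** Five visits in three groups make up to 15 comparisons, any of which could support a statement that a group met the primary endpoint. The Bonferroni step deals with visits inside one group. It leaves three separate chances of success across groups, two of them in controls, and it lowers the power at each visit.

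The verdicts also answer a different question from the one the trial asks. The Synopsis objective and Protocol 1.2 and 3.1 concern what the insert adds relative to Restasis alone and to Restasis with Lotemax. Change from baseline within one arm cannot show that, whichever visit is used.

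At stake is what a positive or a negative primary result would mean.

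**Working it through.** The documents give no power, effect size, design SD or family-wise error rate, so there is no design figure to reproduce.

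**Inputs from the documents.** Threshold 0.05, three groups, five listed visits of which three are reported. Group sizes are 10, 11 and 9 patients (20, 22 and 18 eyes). Loteprednol corneal staining is 0.8 ± 1.5 at baseline and 0.0 ± 0.0 at week 8, reported P = 0.06.

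**Assumptions.** Two-sided tests, independent groups, normal data in the simulations, and the effect sizes and correlations named below.

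**1. Chance that at least one group meets the endpoint when nothing changes**

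- Either direction, each group held at 5%: 1 − 0.95³ = 14.3%.
- As 15 independent tests at 0.05/5 = 0.01: 1 − 0.99¹⁵ = 14.0%. With three visits per group, nine tests at 0.05/3: 14.0%. The divisor hardly matters here.
- Improvement only, each group at 2.5%: 1 − 0.975³ = 7.3%, against 2.5% for a single two-sided 0.05 test.
- Simulation with visits sharing one baseline (between-visit correlation 0 to 0.8, patient as unit): about 13% either direction, 6.5% to 6.9% improvement only.
- Simulation with both eyes analysed as independent (assumed between-eye correlation 0.5 to 0.8, between-visit correlation 0.5): 35% to 53% either direction, 19% to 30% improvement only.

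**2. Which divisor was used?** Loteprednol at week 8 allows a check. Every eye reported there scored zero, so if all eyes were seen the SD of change equals the baseline SD. The check assumes a paired t-test with that SD.

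- 22 eyes: t = 0.8 / (1.5/√22) = 0.8/0.320 = 2.50, raw P = 0.021. Times 3 is 0.062; times 5 is 0.104.
- 11 patients, same mean and SD: t = 0.8 / (1.5/√11) = 1.77, raw P = 0.107 before any correction.

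The reported 0.06 fits 22 eyes and three comparisons best. Rounding leaves five just possible: a change of 0.85 with SD 1.45 gives 0.012 × 5 = 0.060.

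**3. Power at one visit, within one group of 10 patients** (paired t-test, noncentral t; effect in SDs of the change)

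| Assumed change | 0.05 | 0.05/3 | 0.05/5 | 0.05/15 |
|---|---|---|---|---|
| 1.0 SD | 80% | 60% | 50% | 31% |
| 0.8 SD | 62% | 40% | 31% | 17% |
| 0.5 SD | 29% | 15% | 10% | 5% |

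The last column divides by all 15 comparisons. That would bring the error across groups to 1 − (1 − 0.05/15)¹⁵ = 4.9%, but with little power left.

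**The case against.** Several points on the other side stand.

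- **14% is not the chance of a false claim of benefit.** A reader might infer that it is, but it counts significant worsening as success. The Discussion gives the direction as improvement, so about 7% is the nominal figure. Nor is there no rule at all: a direction and a threshold exist. What is missing is the deciding visit, the size of change and control across groups.
- **A five-way split is not documented.** It is a natural inference from five listed visits, but the SAP states no divisor and the one checkable P-value fits three better.
- **The effect sizes are assumptions, and 1 SD may be generous.** In the insert group 70% of eyes had no corneal staining at baseline and could not improve. Improvement per eye is then capped at √(0.3/0.7) = 0.65 SD, although patient-level values could be higher if the two eyes are weakly correlated. If eyes were counted as independent, the nominal loss at 1 SD with n = 20 is small, 99% to 93% at 0.01, but that analysis has its own validity problem.
- **Weeks 8 and 12 are not wasted.** One might infer this because both steroid courses have ended by then. But Restasis continues to week 12 and durability is a fair question. The stated rationale of a faster response also makes weeks 1 and 2 plausible.
- **No group was declared to have met the endpoint,** and the report calls itself a pilot with efficacy unclear.

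These points limit the size of the problem. They do not supply a deciding visit, a rule across groups or a comparison between groups.

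**Conclusion.** The concern holds in this form: the primary can be met in any of three groups, at any of up to five visits, without control across groups and without a test of the comparison that the trial was set up to make. The nominal error is about 14% either direction and about 7% for improvement, assuming valid tests and independent groups, and higher if paired eyes were analysed as independent.

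The power cost is real at either divisor: from 80% to 60% or 50% at 1 SD, and from 62% to 40% or 31% at 0.8 SD, for 10 patients under assumed effects.

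Two stronger readings are not supported. The false-positive risk did not alter the reported primary conclusion, because that conclusion was negative in all three groups. Nor do the documents show that splitting across visits is the main reason for low power: the SAP Discussion itself points to small groups and to entry criteria that did not require corneal staining, and the effects of these have not been weighed against each other.

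**What to change.** In Protocol 2.1 and the SAP's Statistical Analysis section:

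1. Name one primary contrast, insert plus Restasis versus Restasis alone, on change in corneal staining at one named visit, tested at two-sided 0.05 with the patient as the unit (for example, the mean of the two eyes).
2. Justify the visit. Week 4 is reasonable: at day 28 ± 3 it is the last scheduled visit at about the end of the stated 30-day release and the one-month Lotemax course. It is not the only defensible choice.
3. Reserve the statement that the primary endpoint was met for that contrast.
4. Report all other visits and groups as supportive estimates with 95% confidence intervals. State the number of comparisons in any correction that remains.
5. For data already seen, label the choice of visit and contrast as post hoc.

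The cost is wording and a short reanalysis, with no new data. The other four visits and the loteprednol comparison become supportive only, and with 10 and 9 patients the primary contrast will be imprecise, which its confidence interval will show.
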